Heredity spinocerebellar diseases are a group of disorders in which cerebellar degradation manifests in ataxia, a neurological sign causing impaired coordination and balance.¹ The diseases are devastatingly debilitating with many individuals requiring wheelchairs for locomotion after only 10 to 15 years from initial diagnoses. With no disease modifying medications currently available, balance training is recommended to improve motor skills and maintain function. Yet, recent emerging evidence from our research group shows that aerobic training is a promising treatment option. The goal of this study is to compare the impact of balance versus aerobic training on the brains of individuals with hereditary spinocerebellar diseases. Prior research has used clinical measures, such as the Scale for the Assessment and Rating of Ataxia (SARA), to determine the benefits of training. Although validated for this purpose, these scales

cannot differentiate between functional compensation of deficits versus slowing of cerebellar degradation. Thus, it is important to examine the neurological impact of different training methods to distinguish whether one training method is better able to slow disease progression than the other. Moreover, we speculate that aerobic and balance training impact the brain via different mechanisms. Two hypotheses exist regarding the neural effects of training; the degenerating cerebellum undergoes neuroplastic changes to adapt its functioning, or alternatively, other brain areas undergo neuroplastic changes to compensate for deficits. We hypothesize that balance training causes improvements for people with cerebellar degeneration by impacting brain structures outside the cerebellum whereas aerobic training induces neuroplastic changes within the cerebellum. We expect this result because:

1) A 2-week balance training program resulted in increased grey matter volume in the premotor cortex of individuals with cerebellar degeneration, but no statistically significant changes in the cerebellum.

2) Ataxic animals that regularly perform aerobic exercise have larger cerebellums with increased synapses and dendrites at death than those who are sedentary.

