Exploratory Aim 3) To examine the effects of exercise on cerebellar microstructure and functional connectivity to the cerebellum. Diffusion weighted imaging and resting state fMRI scans will be taken before and after individuals with spinocerebellar disease participate in a 6-month home aerobic or balance training program. We will then use the cerebellum as our region of interest to analyze how training impacts cerebellar microstructure and functional cerebellar connections. Although the impact of training on the cerebellum has been investigated in healthy individuals, it is unclear how training will impact the degenerating cerebellum in our subject population. Thus, we will use this preliminary data to determine which cerebellar regions and functional networks are most impacted by training to form targeted hypotheses for future research projects.

STUDY DESIGN

This is a single-blinded randomized control trial. After initial testing, participants will be randomly assigned to either home balance or aerobic training for 6 months. After training, individuals will undergo post-training testing. At the post-training testing, individuals will be encouraged to continue training, but not required to as part of the study. Follow-up testing will then be conducted at 3- and 6-month post-training to evaluate the longevity of training effects.

The rationale for this study design is as follows:

1) Randomization between balance and aerobic training groups will balance known and unknown confounding factors that may influence changes in cerebellar volume. Individuals

conducting assessments will be blinded to group, but participants cannot be blinded given the nature of the intervention.

2) Although the use of an active control (balance training) as opposed to a placebo control may make it more difficult to detect differences between groups, our preliminary data made us comfortable that we would be able to detect differences. This design also allows us to examine the neural mechanisms underlying balance training effects on individuals with spinocerebellar disease in addition to aerobic training.

3) 6-months of training was used for this study because prior work in our laboratory on healthy individuals showed that 6-months of training was long enough to detect statistically significant changes in brain volume.

4) Follow-up testing was selected to start at 3 months post-training because our prior research showed that clinical effects were still seen at this timepoint.

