Resting State Functional MRI: This measure will be a primary outcome for Aim 3. The anatomical and functional data will be pre-processed and analyzed using Statistical Parametric Mapping (SPM12) and the CONN toolbox Version 14p. Functional data will be pre-processed using a slice scan time correction, realignment (motion correction), registration to structural images and spatial normalization to Montreal Neurological Institute (MNI) standardized space, smoothing with a Gaussian filter of 5.0 mm spatial full width at half maximum value. A conventional band-pass filter over a low-frequency window of interest (0.008–0.09) will also be applied to the resting-state time series. After these preprocessing steps, we will extract signal to noise from the white matter and cerebrospinal fluid by principal component analysis without affecting intrinsic functional connectivity. These components, white matter, cerebrospinal fluid, and motion parameters, will be included in the model and considered as covariates of no-interest.

To determine the region of interest within the cerebellum, a localizer scan will be performed after resting fMRI as described in MRI acquisition. We focused on the legs because gait abnormalities are the main deficits in individuals with spinocerebellar ataxia. The coordinates of the region of interest within the cerebellum will be selected on the basis of activation peaks obtained from the block design analysis. For each subject, we will obtain the mean BOLD signal of the region of interest by defining a mask around the seed in the standard space. To ensure that distortion was not present in localizer scans, we will verify that head motion does not exceed a threshold of 1mm and run a general linear model with predictors associated with the movement conditions to ensure there is not activation of voxels outside the brain.

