All analysis will be conducted blind to which intervention is being evaluated. SAS (version 9.4) will be used for all statistical analyses. We will use intention to treat principles. Demographic and clinical variables will be compared using the Wilcoxon's test and chi-squared analysis for continuous and categorical variables, respectively. The association between cerebellar volume change and SARA score change will be estimated with Spearman's correlation coefficient. We will use linear mixed-effect regression analysis to test whether change in cerebellar volume differed between training groups, controlling for age and other co-variates mentioned above as fixed effect. To account for within-subject correlation due to repeated measurement, we will include a random

intercept. If the assessment effect is significant ($p < 0.05$), post hoc analysis will be performed using pairwise comparisons between assessments.

For diffusion tensor imaging, individual ANCOVAs will be determined for FA and MD in the middle of both hemispheres for the regions of interest, with age, gender, and disease type as covariates.

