For resting fMRI analysis, the mean BOLD time course of the regions of interest will be used as a predictor in a multisubject general linear model to evaluate the functional connectivity of that seed with every voxel in the brain. In addition, to account for potential contributions of physiological noise, the time course of nuisance signals of white matter, cerebrospinal fluid, and six motion parameters will be included as predictors in the same general lineal model. The analysis will end with an activation map of all voxels in the brain that correlate with the seed of interest. We will minimize detection of false positives by using a cluster-corrected family wise error rate correction at $p < 0.05$. The correction procedure will use Monte Carlo simulations to calculate the probability of having a cluster of a certain size being due to chance alone. Our z-statistic images will then be projected onto the inflated template brain. The analysis will be conducted separately for pre-training and post-training scans. For further group analysis, we will use random-effects analysis to compute comparison before and after training. To investigate the strength of connectivity changes at the single-subject level, we will calculate the values for each voxel underlying the connectivity maps in individual participants. These values will represent the strength of connectivity between the seed area and individual voxels. Analyses of the distribution of the values across subjects will be done to estimate connectivity patterns.

Sample Size Calculation: 11 subjects had completed our preliminary study with structural MRI scans before and after training. The data shows a change in cerebellar volume of $-1.06\% \pm 0.53$ for the balance group, and a cerebellar volume increase of $+1.28\% \pm 1.04$ for the aerobic group. The calculated effect size was 2.34. Setting $\alpha = 0.05$ and $\beta = 0.2$ and using a conservative effect size of 1.34 and a standard deviation of 1.3 (as seen in our pilot data), we determined that we will require 16 subjects per group for this study.

Dropout and Compliance Rate: In our current study looking at 6 months of balance verse aerobic training in this population, we currently have a drop-out rate of 11.8%. Using a slightly higher drop-out rate of 20%, we will require 20 subjects per group. In addition, 85% of participants in our pilot study met training goals. Studies with similar training programs show more modest

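### The resting-state fMRI plan compares only before with after training and never tests aerobic against balance; the DTI model is under-specified and leaves out baseline

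*Combined protocol and SAP*

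**What the plan says.** All places are in the combined protocol and SAP.

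- **Goal.** Study Purpose and Rationale sets out to "compare the impact of balance versus aerobic training on the brains of individuals with hereditary spinocerebellar diseases" and hypothesises that the two trainings act on different brain structures.
- **Design.** Participants are randomised to home balance or home aerobic training. Study Design, rationale 2, describes "the use of an active control (balance training) as opposed to a placebo control", so there is no untrained arm.
- **Status of the outcome.** Study procedures, Resting State Functional MRI: "This measure will be a primary outcome for Aim 3". Research Aims & Abstracts labels Aim 3 exploratory, with the purpose to "determine which cerebellar regions and functional networks are most impacted by training to form targeted hypotheses for future research projects".
- **fMRI analysis.** Statistical Procedures builds seed-to-voxel maps by time point: "The analysis will be conducted separately for pre-training and post-training scans". It continues: "For further group analysis, we will use random-effects analysis to compute comparison before and after training". Single-subject connectivity values are then described across subjects. Training arm is not mentioned in any of these steps.
- **Volume analysis, same section.** The mixed model is there to "test whether change in cerebellar volume differed between training groups".
- **DTI analysis, same section.** Separate ANCOVAs are planned for FA and MD "for the regions of interest, with age, gender, and disease type as covariates". The text does not say whether the response is the post-training value, the change or both scans. It does not name training group as the factor, and it does not list baseline FA or MD, although diffusion scans are taken before and after training.

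**The concern.** A before/after comparison does not estimate the difference between the arms. With two active arms it also cannot attribute a change to training, because degeneration over six months and repeat scanning are part of the same change. The text does not say whether the arms are pooled or analysed separately, and neither reading tests the arm difference.

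- **Pooled:** effects in opposite directions cancel, and a change caused only by progression or rescanning can be reported as a training effect.
- **Separate:** one arm's map can reach significance and the other's not when both arms truly change by the same amount. The pair of maps then invites a conclusion about arm differences that no test supports.

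At stake is which regions and networks are carried forward into later research. The DTI point is smaller. As written, two analysts could fit different models, and a strong predictor that is already collected goes unused.

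**Working it through.** **Inputs.** From Statistical Procedures, Sample Size Calculation: pilot volume change -1.06% (SD 0.53) for balance and +1.28% (SD 1.04) for aerobic; planning difference 1.34, SD 1.3, alpha 0.05, power 80%, 16 per group. Two-sided testing and equal allocation are assumed. The documents give no connectivity effect, no connectivity SD and no baseline-to-post correlation for FA or MD, so those enter as assumptions.

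**1. The plan's own figure.** Standardised difference = 1.34/1.3 = 1.03. A two-sample t test at 80% power needs 15.8, so 16 per group, with power 80.5% at 16. The stated 16 reproduces. It was derived for volume; no calculation is given for fMRI or DTI.

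**2. Arms analysed separately, equal true change.** If each arm's test has power p, exactly one is significant with probability 2p(1-p).

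- p = 0.8: 2 × 0.8 × 0.2 = 0.32
- p = 0.5: 2 × 0.5 × 0.5 = 0.50

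A direct group-by-time test at the 0.05 level would be falsely positive 5% of the time.

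**3. Arms pooled, opposite changes.** The pilot volume figures serve here only as an illustration; they are not connectivity data.

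- Pooled mean change = (-1.06 + 1.28)/2 = +0.11%
- Arm difference = 1.28 - (-1.06) = 2.34 points
- Average within-arm SD = √((0.53² + 1.04²)/2) = 0.825

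At 16 per arm, a one-sample t test on the pooled changes rejects in 0.07% of 100,000 simulated trials. A two-sample t test between arms has power above 99.9%.

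**4. Arms pooled, common change from progression only.** With n = 32, a one-sample t test has 80% power at 0.51 SD of change. A shift of that size, identical in both arms and unrelated to training, would usually be declared a before/after effect.

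**5. Sensitivity of each contrast** (80% power, two-sided 0.05, single test, before family-wise error correction):

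| Contrast | n | Detectable effect (SD of change) |
|---|---|---|
| Before/after, arms pooled | 32 | 0.51 |
| Before/after, one arm | 16 | 0.75 |
| Arm difference in change | 16 per arm | 1.02 |

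**6. DTI: value of baseline as a covariate.** Let r be the partial correlation of baseline with post-training value given age, gender and disease type. The variance of the arm difference with baseline included, relative to the model without it, is 1 - r² when the response is the post value, and (1 - r²)/(2 - 2r) = (1 + r)/2 when it is the change score.

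| Assumed r | Ratio, post value | Ratio, change score |
|---|---|---|
| 0.6 | 0.64 | 0.80 |
| 0.7 | 0.51 | 0.85 |
| 0.8 | 0.36 | 0.90 |
| 0.9 | 0.19 | 0.95 |

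Across r from 0.6 to 0.9 the variance therefore falls by 36% to 81% against a post-only model, and by 20% down to 5% against a change-score model.

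**The case against.** Aim 3 is exploratory and asks how training affects microstructure and connectivity, without a between-arm hypothesis of its own. A before/after map speaks to that wording. This limits the severity and protects Aim 1, but with no untrained arm the map still cannot attribute change to training, and the study-level goal and mechanism hypothesis are comparative.

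Statistical Procedures also says that all analysis is blind to intervention, which suggests that the arms are kept apart. That makes the pooled reading less likely. It does not supply a test of the arm difference, and step 2 then applies.

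The numbers have limits, and these objections stand. The pooled illustration borrows pilot volume changes from 11 subjects that are nearly equal and opposite, which is close to a worst case. The expression 2p(1-p) peaks at 50% and falls to 9.5% at 5% or 95% power, and it treats each arm as one test when the plan is voxel-wise. The figures show the mechanism; they do not forecast this fMRI analysis. The 1.02 SD detectable difference would be larger after whole-brain correction, by an amount that the documents do not allow one to compute.

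On DTI, FA and MD are named as measures, and an ANCOVA in a two-arm trial may be taken to imply arm as the factor. What is missing is the form of the response, an explicit factor and the baseline covariate. Omitting baseline does not bias the randomised comparison.

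**Conclusion.** The concern holds. The only second-level resting-state fMRI comparison in the plan is before versus after training. Followed as written, it can neither separate training from six months of progression and rescanning nor show that the arms differ. This is a stated analysis that does not answer the comparative question, and the same section gives cerebellar volume the test that fMRI lacks.

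The size depends on the reading: with separate arms and equal true change, 32% to 50% discordant results for per-arm power of 80% to 50%; with pooling, cancellation of opposite effects, or a progression-only shift of 0.51 SD flagged with 80% power. All rest on single-test approximations with 16 evaluable participants per arm.

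The DTI point is secondary: under-specification, with a precision gain that depends on assumed correlations of 0.6 to 0.9. The change should be made. It affects what Aim 3 passes to future research and leaves the Aim 1 conclusion untouched.

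**What to change.** **Resting-state fMRI.** State that the second-level test is the group-by-time contrast, that is, the arm difference in post-minus-pre connectivity, under the cluster-level family-wise error correction already planned. Keep the within-arm before/after maps and label them descriptive. The contrast removes change common to both arms; it will not show an effect against no training, which this design cannot provide.

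**DTI.** State the model for each region as post-training FA (or MD) = training group + baseline FA (or MD) of the same region + age + gender + disease type, and report the group effect with a 95% confidence interval.

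**Cost.** Analysis wording only, using scans already planned, and one degree of freedom per DTI model. The arm contrast is less sensitive than a within-arm one: about 1.02 SD against 0.75 SD at 80% power, before family-wise error correction. As a single test, 1.02 SD is about the size for which the trial is planned in Aim 1 (1.03 SD).

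### The planning SD of 1.3 is credited to the pilot, but the pilot values printed beside it do not pool to 1.3 whether ± means SD or SE

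*Combined protocol and SAP*

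**What the plan says.** All of the material is in the Sample Size Calculation paragraph under Statistical Procedures.

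- Pilot size: "11 subjects had completed our preliminary study with structural MRI scans before and after training". The split between the two arms is not given.
- Pilot result, first arm: "The data shows a change in cerebellar volume of $-1.06\% \pm 0.53$ for the balance group".
- Pilot result, second arm: "a cerebellar volume increase of $+1.28\% \pm 1.04$ for the aerobic group". For neither arm does the paragraph say whether ± is a standard deviation or a standard error.
- Pilot contrast: "The calculated effect size was 2.34".
- Planning inputs: alpha 0.05 and beta 0.2; for the difference, "using a conservative effect size of 1.34"; for the SD, "a standard deviation of 1.3 (as seen in our pilot data".
- Result: "we determined that we will require 16 subjects per group for this study".

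The Dropout and Compliance Rate paragraph then raises this number to 20 and to 24 per group, so the recruitment target is built on the 16. The plan does not show how 1.3 was obtained from the pilot.

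**The concern.** The SD is presented as observed, yet it is larger than both ± values printed for the pilot. If those are SDs, no within-arm pooling can exceed the larger of them, 1.04. If they are standard errors, the arm SDs are larger than the printed values by the square root of the arm size and may lie well above 1.3.

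For a given difference, the required sample size grows with the square of the SD, so the source of this one number matters. With ± undefined, a reader cannot tell whether 16 per group is generous or short for the difference the trial is designed to detect.

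**Working it through.** **Inputs.** Balance -1.06 ± 0.53; aerobic +1.28 ± 1.04; 11 subjects in total; planning difference 1.34; planning SD 1.3; alpha 0.05; power 0.80; 16 per group. All are from the Sample Size Calculation paragraph. Assumptions: a two-sided test (sidedness is not stated), 1:1 allocation, and pilot splits of the 11 subjects with at least 2 per arm.

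**Step 1: what 2.34 and 1.34 are.** 1.28 - (-1.06) = 2.34, a raw difference in percentage points. If 1.34 were a standardised effect, 10 per group would suffice (t-test), not 16. So 1.34 is also a raw difference, used with the SD of 1.3.

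**Step 2: reproduce the plan's figure.** Two-sample t-test, noncentrality = difference / (SD × sqrt(2/n)) = 1.34 / (1.3 × sqrt(2/16)) = 2.92 on 30 degrees of freedom. Power is 80.5% at 16 per group and 77.8% at 15. The stated 16 is reproduced. A one-sided test would need 13, so two-sided is the reading that fits.

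**Step 3: pooled within-arm SD from the printed values.** With a balance subjects and b = 11 - a aerobic subjects,

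pooled SD = sqrt{[(a - 1) s1² + (b - 1) s2²] / 9}.

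If ± is SD, s1 = 0.53 and s2 = 1.04. If ± is SE, s1 = 0.53 × sqrt(a) and s2 = 1.04 × sqrt(b). Example for a 6/5 split:

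- SD reading: sqrt[(5 × 0.2809 + 4 × 1.0816) / 9] = 0.80.
- SE reading: s1 = 0.53 × sqrt(6) = 1.30, s2 = 1.04 × sqrt(5) = 2.33, pooled 1.83.

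Power is for 16 per group and a difference of 1.34; n is per group for 80% power.

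| Split (balance/aerobic) | ± is SD: pooled SD | power | n | ± is SE: pooled SD | power | n |
|---|---|---|---|---|---|---|
| 2/9 | 1.00 | 95.7% | 10 | 2.95 | 24% | 78 |
| 3/8 | 0.95 | 97.1% | 9 | 2.63 | 29% | 62 |
| 4/7 | 0.90 | 98.2% | 9 | 2.33 | 35% | 49 |
| 5/6 | 0.85 | 99.0% | 8 | 2.06 | 43% | 38 |
| 6/5 | 0.80 | 99.6% | 7 | 1.83 | 52% | 31 |
| 7/4 | 0.74 | 99.9% | 6 | 1.66 | 60% | 26 |
| 8/3 | 0.68 | >99.9% | 6 | 1.57 | 65% | 23 |
| 9/2 | 0.61 | >99.9% | 5 | 1.58 | 64% | 23 |

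The SD column never rises above 1.00 and the SE column never falls below 1.57, so 1.3 lies in the gap between them. Using the larger printed value, 1.04, for both arms gives 94% power at 16 per group and n = 11. Under the SE reading, letting the arms keep different SDs (Welch test) gives 35% to 67%, which does not change the picture.

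**Step 4: other routes to 1.3.**

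- One arm only: under the SE reading with 6 balance subjects, 0.53 × sqrt(6) = 1.30. That is the balance arm alone; the aerobic SD would be 2.33.
- All 11 changes ignoring arm: SD = sqrt{[9 × pooled² + (ab/11) × 2.34²] / 10}, with ± read as SD. This runs from 1.11 to 1.47, and is 1.27 at 8/3 and 1.34 at 2/9. It includes the 2.34-point difference between the arms, so it is not the within-arm SD that a two-group comparison needs.

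**The case against.** The strongest reply is that nothing is wrong with the power. The stated 16 follows from the stated inputs. Under the more common reading of ± as SD, 1.3 exceeds both pilot SDs, so it adds safety. A planning SD above the estimate from a small pilot is sound practice: for the equal-weight pooled SD, sqrt[(0.53² + 1.04²)/2] = 0.825, taken on 9 degrees of freedom, the one-sided 90% and 95% upper limits are about 1.21 and 1.36, which bracket 1.3. The planning difference is also a full point below the observed 2.34. And 24 recruited per group with 20% dropout leave about 19 (24 × 0.8 = 19.2), which at SD 1.3 gives 87% power.

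Most of this stands. A reader might infer from the mismatch that the trial is underpowered, or that the 80% is simply wrong. The documents support neither. Power falls below 80% only if ± is a standard error, and the plan does not say so. The match of 0.53 × sqrt(6) with 1.30 is suggestive, but it needs an arm size that the plan does not report.

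What the reply does not answer is the attribution. The paragraph attaches the word conservative to the 1.34 and presents 1.3 as something observed. An SD ignoring arm might come near 1.3 at some splits, but it would be the wrong quantity to call the pilot SD for this comparison. Nor does the recruitment margin settle the SE reading: with 19 per group and the pooled SDs in the table, power would be about 28% to 73%.

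Calling a raw difference an effect size is loose labelling, not a calculation error; the figures needed to see this are printed in the same paragraph.

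**Conclusion.** The point holds as an error in the stated source of the planning SD. The printed pilot values do not give a pooled within-arm SD of 1.3 under either meaning of ± or at any split of the 11 subjects with at least 2 per arm, and the sample size relies on that number. This part does not depend on an assumed split.

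The consequence for power is conditional. For a 1.34-point difference with 16 per group (two-sided t-test, alpha 0.05):

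- ± is SD: about 96% to nearly 100% (94% with 1.04 in both arms). The 1.3 is then a cautious choice, and only its description is wrong.
- ± is SE: 24% to 65% over all splits, and 43% to 52% at a 5/6 or 6/5 split. The trial would then be short of its stated 80%.

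The documents neither state nor exclude the SE reading, so low power is a possibility to be ruled out, not a finding.

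**What to change.** In the Sample Size Calculation paragraph:

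1. State whether the pilot ± values are SDs or SEs, and give the number of pilot subjects in each arm.
2. Replace the attribution of 1.3 to the pilot with the within-arm SD that follows. If the values are SDs, 1.3 may be kept, described as a deliberately conservative assumption.
3. Restate the power of 16 analysable subjects per group on that SD.
4. Label 2.34 and 1.34 as differences in percentage points of cerebellar volume change.

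The cost is rewording and one recomputation. The restated power may be less favourable than 80% if the values turn out to be standard errors. No extra patients and no change of design or analysis are requested.

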compliance rates of around 75%.⁷²⁻⁷⁴ Using a compliance rate of 75%, we will need to recruit 24 subjects per group. Based on previous studies, we expect to recruit about 24 subjects per year and will plan on 2 years of recruitment.

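### The recruitment target of 24 per group does not follow from 20% drop-out and 75% compliance (dividing gives 27); the stated justification is wrong, but the intention-to-treat analysis is not shown to be under-powered

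*Combined protocol and SAP*

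**What the plan says.** The chain stands in the protocol's STATISTICAL PROCEDURES, under Sample Size Calculation and Dropout and Compliance Rate.

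- Base size: for a difference of 1.34 with standard deviation 1.3, alpha 0.05 and beta 0.2, "we determined that we will require 16 subjects per group for this study".
- Drop-out: the ongoing study has lost 11.8%, and the plan takes a higher figure: "Using a slightly higher drop-out rate of 20%, we will require 20 subjects per group".
- Compliance: the plan first reports its pilot experience, "In addition, 85% of participants in our pilot study met training goals", then notes that similar programmes achieve about 75%, and concludes: "Using a compliance rate of 75%, we will need to recruit 24 subjects per group".
- Timeline: "we expect to recruit about 24 subjects per year and will plan on 2 years of recruitment". That is 48 participants, or 2 x 24.

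The opening paragraph of STATISTICAL PROCEDURES fixes the analysis principle: "We will use intention to treat principles". No inflation formula is printed for either step, and no analysis restricted to compliers is described.

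**The concern.** The size the trial recruits to is 24 per group, and the two-year recruitment period is built on it. Its last step cannot be reproduced from the rates given. A reader therefore cannot tell how much allowance for non-compliance the 24 contains.

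A second gap sits beside the arithmetic. Under intention to treat, non-compliers stay in the analysis and may dilute the group difference. Dividing by a compliance rate counts them as lost, which is a different thing. The plan does not say how compliance enters the sample size, or whether its planning difference of 1.34 already allows for non-compliance.

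**Working it through.** **Inputs** (Sample Size Calculation; Dropout and Compliance Rate): difference 1.34, SD 1.3, alpha 0.05, power 0.80, drop-out 20%, compliance 75%. Rates cited but not adopted: drop-out 11.8%, compliance 85%. Assumed here: two-sided test, equal groups, and a two-sample t-test as an approximation to the planned covariate-adjusted mixed model.

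**Units.** The plan says "The calculated effect size was 2.34". This is 1.28 - (-1.06) = 2.34, a difference in percentage points of volume change. The 1.34 is read on the same scale, so the standardised difference is 1.34/1.3 = 1.03.

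**Step 1, base size.** The t-test gives n = 15.8, so 16 per group, with power 80.5% at 16. The plan's 16 reproduces. (The normal approximation gives 14.8, so 15, which is not the plan's figure.)

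**Step 2, drop-out.** 16/(1 - 0.20) = 20. The plan's 20 reproduces.

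**Step 3, compliance.** 20/0.75 = 26.7, so 27. The plan's 24 does not reproduce. Rounding is not the cause: 15.8/(0.80 x 0.75) = 26.3, also 27. Going from 20 to 24 implies compliance of 20/24 = 83.3%.

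**Other routes, and what each requires:**

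| Route | Result | What it needs |
|---|---|---|
| 16/0.75 | 21.3, so 22 | all drop-outs already counted as non-compliant; the step to 20 is then redundant |
| 16 x 1.2 x 1.25 | 24.0 | multiplying by (1 + rate), which is not a valid inflation |
| 20/0.85 | 23.5, so 24 | the pilot compliance, which the plan replaces with 75% |
| 16/0.882/0.75 | 24.2, so 25 | the observed 11.8% drop-out, which the plan replaces with 20% |
| partial overlap | between 22 and 27 | an overlap of drop-outs and non-compliers that is not stated |

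The multiplication route can be tested by working backwards: 24 x 0.80 x 0.75 = 14.4 compliant completers per group, short of 16.

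**Size of the gap.** 27 - 24 = 3 per group, 6 in total, or 3/24 = 12.5%.

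**What 24 delivers under intention to treat.** 24 x 0.80 = 19.2, about 19 evaluable per group. At n = 19 the t-test has 87.1% power for 1.34, and 80% power for a difference of 1.21.

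**The case against.** The strongest reply is that division is an inference. The plan prints no formula, and its 20 fits 16 x 1.2 = 19.2 rounded up as well as it fits 16/0.80. Carried on unrounded, 19.2 x 1.25 = 24.0, so one simple rule reproduces every printed number. Nor does the text expressly chain the two allowances: its additive connector introduces the 85% pilot rate, not the 75% step, and nothing says that drop-outs and non-compliers are separate people. The figure 24 lies between full overlap (22) and full chaining (27).

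This stands as far as attribution goes: one cannot say that the plan declares a method and then breaks it. It does not rescue the 24. The multiplication rule may explain the number, but it does not deliver the 16 it sets out to protect. Every other route to about 24 needs a rate the plan set aside or an overlap it does not mention.

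The second reply is that little follows in practice, and much of this also stands. Intention to treat needs 20 recruited, and the plan recruits 24. The 14.4 compliant completers would matter directly only for a compliers-only analysis, and none is planned.

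A reader might go further and infer that the trial is under-powered because non-compliers dilute the effect. That requires 1.34 to be a difference among compliers only, which the documents do not say. They lean, if anything, the other way. The pilot difference came from a study in which 85% met training goals. It was then cut from 2.34 to 1.34, whereas a full 25% dilution would leave 0.75 x 2.34 = 1.755. The planning SD of 1.3 also exceeds both pilot SDs (0.53 and 1.04).

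**Conclusion.** The target of 24 per group does not follow from 20% drop-out and 75% compliance. Standard inflation gives 27, or 22 if all drop-outs already count as non-compliant. This is an error in the stated justification of the recruitment figure and should be corrected.

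Three stronger conclusions are not supported:

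- **That the intention-to-treat analysis is under-powered.** About 19 evaluable per group exceeds the 16 required, with 87% power if 1.34 is the intention-to-treat difference.
- **That the trial must enrol 6 more.** The 27 shows the inconsistency. It is not a requirement of the planned analysis.
- **That the 4 per group above 20 were meant as a margin for non-compliance.** The documents do not reveal how 24 was reached.

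The power figures assume a two-sided 5% t-test, SD 1.3 and 20% drop-out. What remains open is whether 1.34 already allows for imperfect compliance; only the sponsor can say.

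**What to change.** Keep 24 per group and the two-year recruitment plan. In Dropout and Compliance Rate:

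1. Delete the statement that 75% compliance leads to 24, or have the sponsor give a corrected derivation.
2. State what 24 delivers. For example: *Twenty-four participants per group will be randomised. With 20% drop-out, about 19 per group will be evaluable, giving 87% power for an intention-to-treat difference of 1.34 percentage points (SD 1.3) and 80% power for 1.21.*
3. State that 24 does not provide 16 compliant completers per group if 75% compliance applies on top of 20% drop-out (14.4 expected).
4. State whether 1.34 is meant as the intention-to-treat difference, and label 2.34 and 1.34 as percentage-point differences.

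The cost is wording only: no added participants, no longer recruitment and no change to the analysis. The one drawback is that the justification reads slightly less favourably, because it no longer claims that 24 fully covers 75% compliance.
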